## **2.5 Secondary Objectives**

- Overall Survival at 30 days is a key secondary endpoint.
- Improvement in inflammatory markers associated with cytokine storm (Ferritin, C-Reactive Protein (CRP), d-dimer, white blood cell count)
- Cumulative incidence of grade 3 and 4 adverse events during hospitalization
- Cumulative incidence of serious adverse events during hospitalization
- Duration of hospitalization
- Duration of ventilation
- Ventilator free days (reintubations or death within 28 days will result in zero ascribed time off ventilator prior to reintubation)
- Improvement in oxygenation or paO2/FIO2 ratio

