### **3.2 Inclusion Criteria (applicable for patients enrolled for treatment or data collection)**

- Age 18 years or older
- Confirmed COVID-19 infection
- Evidence of cytokine storm defined as:
  - Peak ferritin > 10,000 ng/mL OR
  - Peak ferritin > 500 ng/mL and one or more of the following at any time during hospital admission:
    - Lactate dehydrogenase > 500 U/L, d-dimer > 1000 ng/mL, C-reactive protein > 100 mg/L, or WBC > 15 k/uL
- Cohort 1: Intubated status as a result of COVID infection-associated respiratory illness
- Cohort 2 (if activated): Evidence of progressive respiratory failure (requiring >4 L/min of supplemental oxygen to maintain SaO2 greater than 92%) without intubation

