## 7. STATISTICAL CONSIDERATIONS

### 7.1 Sample Size Considerations

This study will be performed with two cohorts 1) severe COVID-19 infection and 2) moderate COVID-19 infection (as defined in inclusion criteria).

The effect of the intervention will be evaluated in each cohort separately. A total of 32 patients will be enrolled in each cohort with a 3:1 allocation ratio (24 Etoposide and 8 control per cohort). Assuming a 30% response rate in the control group for the primary outcome of a 2 point improvement in respiratory status on an 8 point scale at Day 14, we can detect a 50% increase in response in the Etoposide group (80% response rate in the Etoposide group) with a 2-sided  $\alpha$  of 0.05 and 80% power. While this study is not powered to detect a statistically significant difference in outcome, it will provide initial evidence of efficacy if improvement in response is observed.

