## 7.2 Statistical Analysis

Tabulations overall, and by treatment group, will be produced for appropriate demographic, baseline, efficacy, and safety parameters, with number and percentages reported for categorical variables and the mean, median, standard deviation, and range for continuous variables. All analyses will be performed at an  $\alpha=0.05$  level using SAS v.4.

Efficacy analyses will be performed in an intention-to-treat (ITT) population consisting of all patients randomized. The difference in ordinal scale improvement rates between treatment arms will be calculated with a 95% confidence interval and formally compared using Fisher's Exact Test. For secondary analysis of the primary endpoint, logistic models individually adjusted for age, diabetes, chronic lung disease/moderate or severe asthma, immunocompromise, liver disease, heart disease/hypertension, smoking and obesity (BMI  $> 40$ ), residence in long-term care facility, will also be examined with odds ratios and 95% confidence intervals reported.

The analysis of secondary time to event endpoints including survival at 30 days, duration of hospitalization, duration of ventilation and ventilator free days, will be compared between treatment arms based on a log-rank test. The median will be estimated with a 95% CI for each treatment arm using the Kaplan-Meier method. Cox proportional Hazards models adjusted individually for age, diabetes, chronic lung disease/moderate or severe asthma, immunocompromise, liver disease, heart disease/hypertension, smoking and obesity (BMI  $> 40$ ), residence in long-term care facility, will also be examined with odds ratios and 95% confidence intervals reported. Changes in inflammatory markers and in oxygenation or  $\text{paO}_2/\text{FIO}_2$  ratio, based on available recorded measurements, will be compared between treatment arms using a two sample t-test, or a Wilcoxon Rank Sum test, as appropriate. Incidence of grade 3 or 4 AEs and serious AEs will be compared using Fisher's Exact test.

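### Changes in inflammatory markers and P/F are compared without baseline adjustment and at no fixed day: ANCOVA would gain precision, and deaths need a separate analysis

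*Combined protocol and SAP*

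**What the plan says.** Section 2.5 lists "Improvement in inflammatory markers associated with cytokine storm" as a secondary objective and names ferritin, CRP, d-dimer and white cell count. It gives no time point. Improvement in oxygenation or P/F is a separate item in the same list.

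Section 7.2 tests the changes in these measures "based on available recorded measurements, will be compared between treatment arms using a two sample t-test, or a Wilcoxon Rank Sum test, as appropriate". The covariate-adjusted models in that section are for the primary endpoint (logistic) and the time-to-event endpoints (Cox), and none contains a baseline marker value. The same section states: "Efficacy analyses will be performed in an intention-to-treat (ITT) population consisting of all patients randomized".

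Section 7.1 adds: "The effect of the intervention will be evaluated in each cohort separately". Each cohort has 24 etoposide and 8 control patients.

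The calendar in section 6 schedules the markers at Screening, on Days 1, 4 and 7, before discharge, and at Day 30 as feasible. In the etoposide arm the Day 1 and Day 4 samples precede that day's dose. P/F is scheduled for cohort 2 only, which section 7.2 does not mention.

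**The concern.** The trial's rationale is that etoposide suppresses the cytokine storm, and these markers bear on it most directly. With 8 controls per cohort, precision is scarce. An unadjusted comparison of changes gives up some of it, although the Day 1 value needed for adjustment is already collected.

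The comparison is also not fully defined. Two candidate baselines (Screening, Day 1), four follow-up times (Day 4, Day 7, before discharge, Day 30) and two tests give 2 × 4 × 2 = 16 versions per marker, before any choice of scale. In an open-label trial that choice is better made in advance.

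Finally, a patient who dies before the chosen day has no value for that day. If mortality differs by arm, the patients left in the comparison are selected differently in the two arms, and section 7.2 gives no rule for this.

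**Working it through.** **Inputs from the documents.** 8 control and 24 etoposide patients per cohort, N = 32, cohorts analysed separately (section 7.1); level 0.05 (section 7.2); measurement days (section 6). The plan states no power or precision for the marker or P/F analyses, so it has no figure to reproduce here. The power statement in section 7.1 concerns the respiratory response.

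**Assumptions (not in the documents).** Correlation ρ between baseline and follow-up of 0.3, 0.5 or 0.7; the same SD, s, at both times and in both arms; approximate normality on the analysis scale; complete data in steps 1 and 2.

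**Step 1: precision.** With k = 1/8 + 1/24 = 1/6:

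- Difference in mean change: variance 2(1 − ρ)s²k.
- ANCOVA with a known slope: variance (1 − ρ²)s²k.
- Ratio: (1 − ρ²) / [2(1 − ρ)] = (1 + ρ)/2.

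Estimating the slope multiplies the ANCOVA variance by 1 + 1/(N − 4) = 29/28 = 1.036 on average.

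| ρ | (1 + ρ)/2 | × 29/28 | Inverse | Worth, in extra patients |
|---|---|---|---|---|
| 0.3 | 0.65 | 0.673 | 1.485 | 49% |
| 0.5 | 0.75 | 0.777 | 1.287 | 29% |
| 0.7 | 0.85 | 0.880 | 1.136 | 14% |

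**Step 2: what this means for power.** For an assumed true effect of one baseline SD, 10,000 simulated trials of 8 against 24 at two-sided 0.05, with the slope estimated, gave:

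| ρ | Change-score t-test | ANCOVA |
|---|---|---|
| 0.3 | 51.2% | 68.5% |
| 0.5 | 65.6% | 77.6% |
| 0.7 | 86.8% | 90.7% |

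**Step 3: selection by death.** A simulation of 1,000,000 patients per arm had no marker effect, ρ = 0.5, and death related to the follow-up marker with correlation r. Only survivors were compared. Shifts are etoposide minus control, in baseline SDs; a positive shift makes etoposide look worse.

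| Deaths, control / etoposide (assumed) | r | Shift, change score | Shift, baseline-adjusted |
|---|---|---|---|
| 40% / 20% | 0.3 | 0.043 | 0.065 |
| 40% / 20% | 0.6 | 0.086 | 0.131 |
| 30% / 15% | 0.3 | 0.031 | 0.048 |
| 30% / 15% | 0.6 | 0.067 | 0.101 |
| 30% / 30% | 0.3 or 0.6 | about 0 | about 0 |
| 20% / 40% | 0.3 | −0.043 | −0.066 |
| 20% / 40% | 0.6 | −0.086 | −0.131 |

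The arm with more deaths looks better among survivors. The shift is small beside the change-score difference detectable with 80% power at ρ = 0.5, which is 1.18 SD. Baseline adjustment does not remove it; in these settings it enlarges it.

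**The case against.** The strongest reply is that nothing here is invalid. Under randomization with complete data, the change-score comparison is unbiased and the t-test holds its level; chance baseline imbalance is already in the standard error. The endpoints are secondary, section 7.1 itself says the study is not powered for a significant difference, and the key secondary endpoint is 30-day survival. At ρ = 0.7 the power gain is under 4 points (86.8% to 90.7%). The variance ratio applies to the t-test; nothing was calculated for the rank-sum option. All of this stands, and it makes the first part of the point one of efficiency.

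Four stronger readings are tempting, and the documents do not support them.

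- A reader might infer that the baseline is discarded. It is not: a change score uses it by subtraction, only less efficiently than a fitted slope.
- A reader might infer that only survivors still in hospital are compared. The calendar schedules a value before discharge and seeks Day 30 values afterwards. The set is patients with a recorded value at an unstated time.
- A reader might take the ferritin cut-offs in section 3.2, just over 500 by one route and "Peak ferritin > 10,000 ng/mL OR" by the other, as a 20-fold baseline spread that dominates raw change. They are cut-offs for the peak during admission and do not describe Day 1 values or the other markers. Section 7.2 also does not say that change is on the raw scale.
- A reader might expect ANCOVA to deal with deaths as well. Step 3 shows that it does not.

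**Conclusion.** The point holds as an efficiency improvement plus a separate gap in the handling of deaths. Assuming ρ of 0.3 to 0.7, equal SDs and complete data at N = 32, baseline adjustment reduces the variance of the treatment contrast to about 0.67 to 0.88 of the change-score value, equivalent to about 49% to 14% more patients. The gain is present across that range and shrinks as ρ rises.

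The distortion from unequal mortality is conditional and modest: 0.03 to 0.09 SD for the change score under the assumed death rates, and none if death rates are equal. It matters mainly because it favours the arm with more deaths and because an available-data comparison cannot cover all randomized patients, as the stated ITT population would require. The P/F part applies to cohort 2 only under the calendar. The primary analysis is unaffected.

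**What to change.** In section 7.2, replace the t-test or rank-sum sentence for these endpoints with the following.

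- For each cohort, analyse each marker at one fixed scheduled day by ANCOVA on the log scale, with the log Day 1 value as covariate. Report the adjusted geometric mean ratio with its 95% CI.
- Name the day. Day 7 is a natural choice, with Day 4 as supportive, because the Day 4 sample precedes that day's dose.
- Analyse P/F in the same way in cohort 2 only, and say so.
- For patients discharged alive before the chosen day, use the pre-discharge value.
- Add a rank-based analysis in which deaths before the chosen day are ranked worst, and present it beside the ANCOVA.

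The cost is SAP wording and a little more analysis work. The Day 1, Day 4, Day 7 and pre-discharge values are already scheduled, so no visits, assays or patients are added.

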## **5.4 Etoposide Expected Toxicities and Management**

Reversible myelotoxicity has been uniformly observed to be the major toxicity for VP-16 and to represent the only clinically significant side effect. Following a single IV injection, peak myelotoxicity occurs at seven to nine days. Following daily injections for five to seven days, myelotoxicity is maximal between 12-16 days from the initiation of therapy. Bone marrow suppression is mainly manifested as granulocytopenia, with thrombocytopenia and anemia occurring to a lesser extent. Gastrointestinal toxicities including transient modest nausea, vomiting, and diarrhea, are common. Other reactions could include aftertaste, rash, pigmentation, pruritis, abdominal pain, constipation, and dysphagia. Occasional alopecia is reported. VP-16 does not produce phlebitis or nephrotoxicity. Rarely anaphylactic-like reactions have been reported, as well as, hypotension. The drug is to be infused over 60 minutes in this study to decrease the potential for hypotension, and the blood pressure and pulse will be monitored during the infusion. Occasionally, chills, fever, peripheral neurotoxicity, stomatitis, hepatotoxicity, transient cortical blindness and radiation recall dermatitis may be a result of VP-16 administration. Stomatitis is usually associated with high dose regimens containing etoposide. The occurrence of acute leukemia has been reported rarely in patients treated with VP-16 in association with other antineoplastic agents. Etoposide can cause fetal harm when administered to a pregnant women. It has been shown to be teratogenic in mice and rats. In females of reproductive potential, etoposide may cause infertility and result in amenorrhea. Premature menopause can occur with etoposide. Recovery of menses and ovulation is related to

age at treatment. Males In male patients, etoposide may result in oligospermia, azoospermia, and permanent loss of fertility. Sperm counts have been reported to return to normal levels in some men, and in some cases, have occurred several years after the end of therapy Secondary leukemias associated with etoposide have been reported. Women of childbearing potential will be advised to avoid becoming pregnant for at least 6 months after the final dose of etoposide. Males with female partners of reproductive potential will be advised to use effective contraception for 4 months after the final etoposide dose.

Safety of etoposide for use by nursing women has not been established.

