## 6. STUDY PROCEDURES & CALENDAR

REQUIRED STUDIES	Screening	Day 1, Day 4 and Day 7 Σ#	Prior to discharge	Day 30*
PHYSICAL				
History & Physical Exam	X	X	X	X
Height, Weight, Body Mass Index, and Body Surface Area	X			
Vital Signs	X	X	X	X
Toxicity Notation	X	X	X	X
Respiratory Status on 8 point scale ^	X	X	X	X
HISTORY				
Concomitant medicines (including COVID therapies, ie hydroxychloroquine, tocilizumab, anakinra) with date of initiation	X			
Smoking status	X			
Comorbidities	X			
Symptoms, including date of symptom onset	X			
LABORATORY				
Beta HCG (for women of childbearing potential)	X			
CBC with Differential +	X	X	X	X
Comprehensive metabolic panel +	X	X	X	X
Lactate Dehydrogenase	X	X	X	X
D-dimer	X	X	X	X
Ferritin	X	X	X	X
C-reactive protein	X	X	X	X
PaO 2 /FIO 2 (P/F) ratio (cohort 2 only)	X	X	X	X
INR (if on warfarin) Ω	X			
ADDITIONAL TESTING				
Electrocardiogram (ECG)	X			

# For subjects randomized to treatment, the data for Day 1 and Day 4 will be collected prior to the etoposide dose (within 24 hours).

\*Information to be obtained as feasible, if patient has been discharged attempts will be made to obtain the information from the patient's primary care provider. If such results are not available, participant will be contacted by the research nurse to assess toxicities.

^ Mortality assessment (included on the 8 point scale) will also be recorded at Day 14 and 60, in addition to Day 30 mentioned above

+ CBC and comprehensive metabolic panel will be measured at least twice weekly during hospitalization. These tests will also be obtained pre-dose 8, 11, 18, and 25 for those patients who require additional etoposide dosing as described above (Section 4.3 and 5.3)

Ω INR to be repeated at least twice weekly for patients on warfarin

Σ Day 1 of treatment for patients randomized to standard of care (SOC) will be considered the day of randomization

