## 9. ADVERSE EVENTS AND UNANTICIPATED EVENTS

### 9.1 Adverse Event Definition

An adverse event is any untoward or unfavorable physical or psychological occurrence in a human subject, including any abnormal sign (for example, abnormal physical exam or laboratory finding), symptom, or disease temporally associated with the subject's participation in the research, whether or not considered related to the subject's participation in the research.

Toxicity will be scored using CTCAE Version 5.0 for toxicity and adverse event reporting. A copy of the CTCAE Version 5.0 can be downloaded from the CTEP homepage ([HTTP://CTEP.INFO.NIH.GOV](http://CTEP.INFO.NIH.GOV)). All appropriate treatment areas will have access to a copy of the CTCAE Version 5.0. All adverse clinical experiences, whether observed by the investigator

or reported by the subject, must be recorded, with details about the duration and intensity of each episode, the action taken with respect to the test drug, and the subject's outcome. The investigator must evaluate each adverse experience for its relationship to the test drug, its expectedness, and for its seriousness.

The investigator must appraise all abnormal laboratory results for their clinical significance. If any abnormal laboratory result is considered clinically significant, the investigator must provide details about the action taken with respect to the test drug and about the subject's outcome.

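### With 8 controls per cohort, the Fisher comparison of grade 3-4 AEs and SAEs, read as any event per patient, has low power for harm if most intubated controls have an event

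*Combined protocol and SAP*

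**What the plan says.** Section 2.5 lists two safety endpoints among the secondary objectives: "Cumulative incidence of grade 3 and 4 adverse events during hospitalization" and "Cumulative incidence of serious adverse events during hospitalization". Section 7.2 gives the test: "Incidence of grade 3 or 4 AEs and serious AEs will be compared using" Fisher's exact test, at an alpha of 0.05. Sections 2.3 and 7.1 set 24 etoposide and 8 control patients per cohort, and section 7.1 has the effect evaluated in each cohort separately.

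An adverse event is defined in section 9.1 as "any untoward or unfavorable physical or psychological occurrence in a human subject". The definition includes abnormal laboratory findings and does not require relatedness. Section 9.2 counts death, life-threatening events and prolonged hospitalization as serious. Cohort 1 is intubated (section 3.2).

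On expected toxicity, section 5.4 says: "Bone marrow suppression is mainly manifested as granulocytopenia, with thrombocytopenia and anemia occurring to a lesser extent". The footnotes to the section 6 calendar add: "CBC and comprehensive metabolic panel will be measured at least twice weekly during hospitalization", without limiting this to one arm.

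The last paragraph of section 7.2 plans further Fisher comparisons, of drug-related events, physical examinations and laboratory evaluations. Its safety population is everyone who took at least one dose of study treatment.

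**The concern.** Events caused by the illness count equally in both arms. In intubated patients with cytokine storm, a large share of controls may have a grade 3-4 or serious event from COVID-19 alone. A yes/no comparison per patient then has little room to show an excess on etoposide, and 8 controls leave few tables that can be significant. Myelosuppression, which section 5.4 calls the major toxicity, would be diluted in the all-cause count.

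Safety is a stated purpose of the trial (section 2.1). A non-significant result could be taken as reassurance when the comparison had little chance of showing harm.

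**Working it through.** **Inputs.** From the documents: 24 vs 8 per cohort (2.3, 7.1), Fisher's exact test and alpha 0.05 (7.2). Section 7.1 says two-sided for the primary outcome. Sidedness is not restated for the safety test, but one- and two-sided p-values are the same when all 24 etoposide patients have an event. Assumed: the control event rate, the etoposide toxicity rates, and the reading of incidence as at least one event per patient.

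**The plan's own power figure.** Section 7.1 states 80% power for the primary outcome only (30% vs 80%). The unpooled normal approximation comes close: SE = √(0.3×0.7/8 + 0.8×0.2/24) = 0.181, and Φ(0.5/0.181 − 1.96) = 78.7%. The planned Fisher test, enumerated exactly, gives 67.9%. No power is stated for the safety comparison.

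**Step 1: the ceiling.** If all 24 etoposide patients and k of 8 controls have an event, all 8−k event-free patients are controls, so p = C(8, 8−k)/C(32, 8−k).

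- k=5: 56/4960 = 0.0113
- k=6: 28/496 = 0.0565
- k=7: 8/32 = 0.25
- k=8: 1

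At k=5, at least 23/24 on etoposide is needed for p<0.05. From k=6 upward, no etoposide count is enough.

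**Step 2: how often the ceiling is met.** With X ~ Binomial(8, q), the chance is P(X≥6). At 100% incidence on etoposide, power is 1 − P(X≥6). The last column assumes that etoposide adds an independent 60% risk, so its event rate is 1 − 0.4(1−q). Power there is by full enumeration of the Fisher test in the direction of harm.

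| Assumed control rate q | P(at least 6 of 8) | Power, 100% on etoposide | Power, added 60% risk (etoposide rate) |
|---|---|---|---|
| 50% | 14% | 86% | 31% (80%) |
| 60% | 32% | 68% | 26% (84%) |
| 70% | 55% | 45% | 19% (88%) |
| 80% | 80% | 20% | 11% (92%) |
| 90% | 96% | 4% | 3% (96%) |

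The last column shows that dilution matters before the ceiling becomes likely.

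**Step 3: a single named toxicity.** With an assumed 5% control rate, exact Fisher power at 24 vs 8 is 84% against 60% on etoposide, 64% against 50%, 35% against 40% and 10% against 30%. Even with 0/8 controls affected, 10/24 on etoposide is needed (p=0.035; 9/24 gives 0.070).

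**Step 4: whether the other planned comparisons cover it.** In the last paragraph of section 7.2:

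- Drug-relatedness is judged open-label by the investigator (2.1, 10.2) and has no meaning for controls, who receive no study drug and no placebo (4.1).
- The all-treated population, taken literally, contains no controls, and section 9.3 starts event reporting at the first dose of study drug.
- The laboratory comparison names no parameter, grade or rule for abnormalities already present at baseline.

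**The case against.** A reader might infer that the test cannot detect even 100% toxicity in the intubated cohort. The documents do not support that as a fact. It requires at least 6 of 8 controls with an event, and no control rate is given. At 50%, power against 100% incidence is 86%. Section 3.3 also excludes some of the sickest patients, such as those on ECMO, continuous renal replacement therapy or more than one vasopressor.

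A reader might also infer that this is the only planned harm comparison. It is not. The last paragraph of section 7.2 reaches laboratory evaluations, where myelosuppression and hepatotoxicity would appear. That objection stands against any claim that specific harms are ignored, but the gaps in step 4 remain.

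Nor should the literal safety population be taken to mean that no control events will be collected. Section 4.1 has controls followed for all secondary objectives, which include these endpoints. The passages need aligning.

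Three further points stand in part:

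- Any event per patient is an interpretation. It is the natural reading of incidence compared by Fisher, but incidence by event term also fits the wording.
- Pooling the cohorts (48 vs 16) would move the ceiling to 14/16 (p=0.0595). However, section 7.1 evaluates cohorts separately and cohort 2 may never open.
- The trial is declared not powered for significance (7.1), and safety oversight rests with the Medical Monitor and the committee review (4.2, 10.2), not on this p-value. This lowers the stakes but does not make the comparison informative.

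Finally, event-specific testing does not restore power in general. The 84% figure needs 60% grade 3-4 neutropenia, while section 1.4 expects no deep or prolonged myelosuppression from two doses.

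**Conclusion.** The point holds as a conditional one and supports a cheap improvement to the analysis plan. The cut-off at 6 of 8 controls is exact for 24 vs 8. How likely it is depends on the unstated control rate: 14% at an assumed 50%, 55% at 70% and 96% at 90%. For an added independent 60% risk, power is at most 31% over that range. These figures rest on the any-event reading, on separate analysis of cohorts and on control events being counted. The further comparisons in section 7.2 point in the right direction but are not defined well enough to fill the gap. The small control arm is the basic limit, and no choice of endpoint removes it.

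**What to change.** In section 7.2:

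- Tabulate any grade 3-4 AE and any SAE by arm, descriptively.
- Replace the drug-related comparison with treatment-emergent grade 3-4 events, meaning new or worsened from the patient's baseline grade and counted whatever the attribution. The list would be neutropenia, thrombocytopenia, anemia and hepatotoxicity (from section 5.4) and infection (section 1.4 raises bacterial super-infection).
- Grade laboratory events from the blood counts and metabolic panels already drawn at least twice weekly in hospital.
- Count control events from randomization, which sections 6 and 8.1 already define as day 1 for that arm, and align the all-treated definition and the section 9.3 reporting window with this.
- Report each risk difference with an exact 95% confidence interval, and state that non-significance will not be read as evidence of safety.

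The cost is analysis-plan wording and a few tables from data already scheduled. The downside is several comparisons in place of two, still with limited power, so estimates and intervals should carry the weight rather than p-values.

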## **4. INVESTIGATIONAL PLAN**

### **4.1 Overall Design**

Open-label, randomized Phase II study of etoposide administered intravenously at a dose of 150 mg/m^2 once daily on Days 1 and 4 for a total of two doses to inpatient patients with moderate and severe COVID-19 who have consented to treatment on this clinical trial. Dose reductions will be performed as outlined in Section 5.

This study includes a screening period, a treatment period, and a follow-up period for adverse events that will include the remainder of hospitalization, with additional assessments at days 30 and 60 as outlined in the study calendar (Section 6). After obtaining informed consent, the patients randomized to etoposide will begin treatment with the study drug. Subjects randomized to control will receive standard of care treatment. No placebo will be used. Subjects will be monitored for adverse events and to evaluate study outcomes. Patients removed from the study due to any unacceptable adverse events will also be followed until time of death or hospital discharge.

For patients randomized to standard of care, day 1 will be considered day of randomization. These patients will be followed to record the outcome of all primary and secondary objectives until time of death or hospital discharge, whichever occurs earlier.

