Additional safety analyses will be based on the reported adverse events and other clinical information. Safety analyses will be performed in the all-treated (AT) population, consisting of all patients who took at least one dose of study treatment. The safety and tolerability of Etoposide will be evaluated by means of drug-related AE reports, physical examinations, and laboratory safety evaluations and compared between groups using Fisher's exact test. The first 10 patients allocated to the Etoposide group in the ventilated cohort will be evaluated for safety endpoints prior to initiating enrollment in the non-ventilated group.

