## 8. MEASUREMENT OF EFFECT

### 8.1 Definitions

**Evaluable for toxicity:** All participants who receive at least one dose of study treatment will be evaluable for toxicity from the time of their first treatment.

**Evaluable for objective response:** Only those participants who have received at least one dose of etoposide will be eligible for objective response.

For purposes of data collection, day 1 of patients on the standard of care arm will be the day of randomization.

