## **9.2 Serious Adverse Event (SAE) Definition**

**Serious Adverse Event:** According to the FDA's Code of Federal Regulations Title 21 Part 314.80, a SAE is any untoward medical occurrence that results in any of the following outcomes:

- Death
- A life-threatening event (an event that places the subject at immediate risk of death from the event as it occurred)
- Inpatient hospitalization or prolongation of an existing hospitalization
- A persistent or significant disability / incapacity
- A congenital anomaly / birth defect
- Important medical events based upon appropriate medical judgment that may jeopardize the patient or subject and may require medical or surgical intervention to prevent one of the outcomes listed in this definition of serious.

**Expectedness:** Unexpected events include any adverse drug experience that is not listed in the current package insert for the drug product (e.g., all previously unobserved or undocumented events).

**Relatedness:** Indicates that a determination has been made that an event had a reasonable possibility of being related to exposure to the product. Examples of causality include not related, unlikely, possibly, probable, definitely related and unable to be determined.

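### The safety set requires a dose of study treatment, so the planned between-group safety test has no controls as worded; adding them would not make its drug-related AE item comparable

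*Combined protocol and SAP*

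**What the plan says.** - **Safety population (Section 7.2).** "Safety analyses will be performed in the all-treated (AT) population, consisting of all patients who took at least one dose of study treatment".
- **What is tested (Section 7.2).** The safety of etoposide is to be judged on "drug-related AE reports, physical examinations, and laboratory safety evaluations and compared between groups", with Fisher's exact test.
- **Toxicity-evaluable set (Section 8.1).** "All participants who receive at least one dose of study treatment will be evaluable for toxicity from the time of their first treatment".
- **Control arm (Section 4.1).** "Subjects randomized to control will receive standard of care treatment. No placebo will be used. Subjects will be monitored for adverse events".
- **Relatedness (Section 9.2).** A related event is one for which it was determined that "an event had a reasonable possibility of being related to exposure to the product".
- **A second AE comparison (Section 7.2, preceding paragraph).** "Incidence of grade 3 or 4 AEs and serious AEs will be compared using" Fisher's exact test. It is not limited to drug-related events and names no population. It serves secondary objectives such as "Cumulative incidence of grade 3 and 4 adverse events during hospitalization" (Section 2.5).
- **Arm sizes (Sections 2.3 and 7.1).** Each cohort has 24 etoposide and 8 control patients.

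**The concern.** Evaluating safety is a stated aim of this randomized study (Section 2.1), and the control arm is what separates harm from etoposide from the heavy background of events in severe COVID-19. Two problems stand in the way.

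1. The population rule admits only patients who have had a dose, and the same paragraph then asks for a comparison of groups. An analyst who follows it literally has nothing to compare etoposide with.
2. Adding the controls repairs only part of this. A patient never exposed to etoposide cannot have an event related to it, so the control count for drug-related AEs is fixed at zero before any data are seen. A small p-value on that item would reflect how many events the investigator attributes to the drug in an open-label trial. It would not show that etoposide patients had more events than standard-of-care patients.

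**Working it through.** The documents give no AE rates and no design figure for the safety comparison. The only inputs taken from them are the arm sizes (24 and 8) and the two-sided 0.05 level.

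**Step 1: the set as worded.** A control takes no dose, so 0 of 8 controls enter the set in each cohort (0 of 16 overall). The two-by-two table has an empty row and Fisher's p is 1.0 for every etoposide count. There is no comparison.

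**Step 2: controls added, drug-related AEs tested.** Section 7.2 does not state the unit, so I assume patients with any drug-related AE. Controls are 0/8 by definition. With x of 24 etoposide patients affected, the two-sided Fisher p-value sums the probabilities of all tables no more likely than the one observed.

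- x = 10: the observed table has probability C(24,10)/C(32,10) = 1,961,256/64,512,240 = 0.0304. Tables with 6, 7 or 8 of the 10 events among controls add 0.0046 + 0.0003 + 0.0000. Total p = 0.035.
- x = 9: the observed table has probability C(24,9)/C(32,9) = 1,307,504/28,048,800 = 0.0466. Tables with 5 or more of the 9 events among controls add 0.0212 + 0.0020 + 0.0001. Total p = 0.070.

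Ten attributed cases out of 24 therefore give p<0.05, and the control arm's actual AE experience does not enter the calculation.

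**Step 3: what drives the result when all-cause risk is equal.** Let r be the all-cause AE rate in both arms and f the share of etoposide patients with an event whose event is attributed to drug. Both are assumed. The drug-related count is then Binomial(24, r × f), and the test rejects when it reaches 10.

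| r (both arms) | f | r × f | Chance of p<0.05, drug-related test | Chance of p<0.05, all-cause test |
|---|---|---|---|---|
| 30% | one half | 0.150 | 0.1% | 2.8% |
| 50% | one half | 0.250 | 5.5% | 3.1% |
| 50% | three quarters | 0.375 | 41% | 3.1% |
| 80% | one half | 0.400 | 51% | 2.4% |
| 80% | three quarters | 0.600 | 98% | 2.4% |

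The last column is the exact rejection probability of Fisher's test on all-cause events, 24 versus 8, at the same equal rate r. It stays below 5% throughout. The drug-related test moves from almost never to almost always rejecting as r and f change, although the all-cause risks are equal in every row.

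**Step 4: what an all-cause comparison can deliver.** At an assumed 18/24 versus 6/8 (75% in each arm) the difference is 0, with a Newcombe 95% CI of about -27 to +36 percentage points. The comparison is valid but imprecise.

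**The case against.** The strongest reply is that the valid comparison is already in the plan. Section 7.2 compares grade 3-4 AEs and SAEs without a drug-related limit, and the objectives in Section 2.5 use a hospitalization window that needs no dose. Section 4.1 follows controls for all primary and secondary objectives, and the Section 6 calendar schedules toxicity notation in both arms. The all-treated rule sits in a paragraph introduced as covering additional safety analyses, so it can fairly be read as applying to those alone. This largely stands: control AE data are evidently intended. What remains is that the all-cause test names no population, and the all-treated sentence speaks of safety analyses without restriction. It can therefore also be read as removing controls from that test.

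A second reply is that controls do have a start date. That is right: Sections 6, 8.1 and 10.1 set their Day 1 at randomization. The first-dose window in Section 9.3 follows a sentence on IRB and FDA reporting and may be regulatory only. A reader might infer that control AEs have no time origin or are not collected; the documents do not support that.

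A third reply is that rejecting on drug-related AEs is not necessarily a false positive. Section 5.4 says "Gastrointestinal toxicities including transient modest nausea, vomiting, and diarrhea, are common", and events truly caused by etoposide are harm. I accept this. A reader might take any high chance of p<0.05 on this item as a false-positive rate, but an assumed drug-related rate alone does not justify that. For this reason Step 3 holds all-cause risk equal and varies attribution, and it includes cases where the test hardly ever rejects.

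The counter-reading that study treatment includes standard of care is weak. The calendar speaks loosely of a first day of treatment for controls, but taking a dose, with no placebo given, points to etoposide.

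**Conclusion.** The point holds and should be fixed. As worded, the all-treated and toxicity-evaluable sets contain no controls, so the between-group test set out with them cannot be done: up to 24 versus 0 per cohort. With the 8 controls added, the examination and laboratory items become comparable but the drug-related AE item does not. Its control count is zero by definition, and 10/24 is enough for p=0.035. The 0.1% to 98% range rests on assumed event rates, assumed attribution shares and a patient-level unit. It shows that the result follows attribution and is not an estimate of what this trial will see.

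Two stronger readings are not supported. The plan does not lack an all-cause safety comparison; it lacks a stated population for it. Nor is patient protection during the trial weakened: the stopping rule in Section 9.5 is based on response, and under Section 10.2 the Medical Monitor receives all AEs and SAEs regardless of relatedness. The consequence is confined to the final safety comparison.

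The Section 8.1 response rule against intention-to-treat, the differing Day 1 definitions, and the end of control follow-up in Section 4.1 against the Day 30 and Day 60 assessments are separate matters. This conclusion does not rest on them.

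**What to change.** 1. In Sections 7.2 and 8.1, define a between-arm safety set that includes all randomized controls, counted from their existing Day 1 at randomization, together with the etoposide patients. The etoposide side may be dosed patients or all randomized patients, and either is defensible. Name one as the main analysis and the other as a sensitivity analysis.
2. State that the all-cause grade 3-4 AE and SAE comparison in Section 7.2 uses this set and is the main between-arm safety comparison. Report the difference with a 95% CI as well as Fisher's p-value. Use the same set for the examination and laboratory comparisons.
3. Report drug-related AEs descriptively in dosed etoposide patients, with no between-group test.
4. In Section 9.3, say whether the first-dose window is for regulatory reporting only, and that AEs in controls are recorded from randomization.

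The cost is wording and slightly more analysis. Controls are already monitored for AEs, and sample size, endpoints and treatment do not change. With 8 controls per cohort the interval will be wide whichever set is chosen.
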